9.2 Secondary Objectives

Secondary objectives are to evaluate the efficacy of the self-administered hypnosis compared to self-administered sham white noise hypnosis for hot flash activity interference, sleep disturbance, anxiety and perception of benefit; with the expectation that there will be significant improvements among participants in the hypnosis group when compared with the self-administered sham white noise hypnosis group. Further, we will evaluate the effects of self-administered hypnosis compared to the self-administered sham white noise hypnosis control at 12 weeks. In order to obtain estimates of the efficacy of the self-administered hypnosis that is not positively biased on the secondary outcome measures, each secondary outcome measure will be analyzed using intent-to-treatment analysis

Hypothesis 2.1

Compared to self-administered sham white noise hypnosis, self-administered hypnosis will result in significant improvements in hot flash activity interference, sleep disturbance, and anxiety at 6 and 12 weeks and perception of benefit at 6 weeks.

Outcome Measures:

- Hot Flash Related Daily Interference Scale
- PROMIS Emotional Distress Anxiety Scale
- Pittsburg Sleep Quality Index
- Subject Global Impression of Change

Additionally, mediators (perceived stress, cortisol, and heart rate variability (HRV) and moderators (hypnotizability and practice adherence) of hot flash reduction will be explored to address the following hypotheses:

Hypothesis 2.2

A decrease in perceived stress will be indicated in the self-administered hypnosis group due to the intervention, which will correspond and contribute to further decrease of the hot flash score at 6 and 12 weeks.

Outcome Measure:

Perceived Stress Scale

Hypothesis 2.3

Diurnal salivary cortisol will demonstrate better circadian rhythms (steeper slopes) in those with larger hot flash reductions and in the self-administered hypnosis group compared to self-administered sham white noise hypnosis at 6 weeks.

Outcome Measure:

• Diurnal Cortisol Rhythm

Hypothesis 2.4

Self-administration of hypnosis and greater hot flash reductions will result in higher resting and 24-hour parasympathetic activity, reflected as higher HRV, compared to self-administered sham white noise hypnosis at 6 weeks.

Outcome Measure:

• Heart rate variability monitor

Hypothesis 2.5

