\pi_{1i} = \beta_{10} + \beta_{11}X_1 + r_{1i}
\beta_{00} = Grand mean hot flash score at baseline for control group
\beta_{01} = Expected difference in hot flash score at baseline between treatment and control groups
X_1 = Value of Treatment indicator (X); 0 = control, 1 = treatment
\beta_{10} = Average amount of change in hot flash score across time for control group
\beta_{11} = Difference in amount of change in hot flash score across time between treatment and control group
r_{0i} = Random error of intercept for participant i adjusted from group assignment [r_{0i} \sim N(0, \tau_{00})]
r_{1i} = Random error of amount of change for participant i adjusted from group assignment [)]
[r_{1i} \sim N(0, \tau_{10})]
Combined (Mixed) Model:
```

The effect of primary interest is the interaction between time and treatment, which is the $\beta_{11}X_1a_{ti}$ term.

 $Y_{ti} = \beta_{00} + \beta_{01}X_1 + \beta_{10}X_1 + \beta_{11}X_1a_{ti} + r_{1i}a_{ti} + r_{0i} + e_{ti}$

Objective #2

Secondary outcomes (activity interference from hot flashes, sleep disturbance, stress, and anxiety) will be entered separately as dependent variables into a similar type of longitudinal regression model described above. The primary difference in models is that for the secondary objectives, one set of models will be estimated using data collected at two points (i.e., baseline & week 6) and another set of models will be estimated using data collected at three time points (i.e., baseline, week 6, & week 12 [follow-up]).

Objective #3

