The focus of Aim #3 is to determine the extent to which cortisol levels, HRV, and perceived stress mediate the relationship between group assignment and hot flashes. For each, we will test the null hypothesis that there is no mediation, or indirect effect, of these potential mediators on the hot flashes although we hypothesize that the relationship between group assignment and hot flashes will be mediated by these variables. Measurement considerations are presented for cortisol levels and HRV followed by a description of the mediation analysis plan. Cortisol levels will be evaluated using a commercial immunoassay with chemiluminescence detection by the CLASS lab at the University of Michigan for all samples from Baylor and Michigan. The lower concentration limits are 0.44 nmol/liter with intra- and interassay coefficients less than 8%. Cortisol slopes will be determined by recording cortisol values at three different times of day for each of the two collection days at baseline and at the end of the intervention, week 6. Higher slope values will reflect flatter diurnal cortisol rhythms. If values are found to be non-normal, we will use log transformations. [99] For HRV, we will extract beat-to-beat (NN) intervals from the recordings collected by the Polar S810. From these, we will use the well-validated Kubios HRV analysis software package[100] to calculate time domain indices of parasympathetic activity (standard deviation of NN intervals, SDNN; and root mean square of standard deviation

of NN intervals, RMSSD) according to standard guideline.^[101] These measures cover both short and longer term recordings and will be collected at baseline and the end of the intervention, week 6.

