Mediation analysis will be performed using a nonparametric bootstrap method, to determine how much of the improvement in the primary and secondary outcomes is mediated by psychophysiological effects of the intervention and by changes in perceived stress. The nonparametric bootstrap method provides more statistical power than traditional mediation analysis and does not require the assumption of normality. Within-subject change in HRV, cortisol slopes and perceived stress scores will be tested as mediators. Average causal mediation effects (ACME) and average direct effects (ADE) will be calculated to compare the mediated and un-mediated portion of the changes in the primary and secondary outcomes between groups. We will also test if pre-trial HRV predicts treatment effects, as we expect that women with high SNS activity at baseline will have the most to gain.

Moderator analysis will be performed using the longitudinal regression models described above. The benefit of using the longitudinal regression model for examining moderation is that the unique contribution of each moderator to the variability between people/groups or to the variability across time can be determined.

Missing Data

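### Section 9.7 plans no arm comparison of week-6 cortisol slope or HRV, so the arm component of H2.3 and H2.4 has no test of its own

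*Combined protocol and SAP*

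**What the plan says.** Section 9.2 words both hypotheses with two components. H2.3 expects steeper cortisol slopes "in those with larger hot flash reductions and in the self-administered hypnosis group compared to self-administered sham white noise hypnosis at 6 weeks". H2.4 expects hypnosis and greater hot flash reduction to raise resting and 24-hour parasympathetic activity, "reflected as higher HRV, compared to self-administered sham white noise hypnosis at 6 weeks". Each names its marker as the outcome measure. Section 9.6.2 describes both markers under Secondary Outcomes, while the synopsis classes the role of the mediators as exploratory.

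Section 9.7 then divides the analyses. Under Objective #2, "Secondary outcomes (activity interference from hot flashes, sleep disturbance, stress, and anxiety) will be entered separately as dependent variables" in the longitudinal model with arm. Perceived stress is on that list; cortisol and HRV are not. Under Objective #3 the plan states that "we will test the null hypothesis that there is no mediation, or indirect effect, of these potential mediators on the hot flashes", and that "Within-subject change in HRV, cortisol slopes and perceived stress scores will be tested as mediators". Results are to be given as average causal mediation effects (ACME) and average direct effects (ADE). One other HRV analysis is named: "We will also test if pre-trial HRV predicts treatment effects". For cortisol there is a transformation rule: "If values are found to be non-normal, we will use log transformations". The covariates of the mediator model are not stated.

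**The concern.** No model in section 9.7 has the week-6 cortisol slope or HRV as dependent variable with arm as predictor. The arm component of H2.3 and H2.4 is a randomised comparison, and so the part of these hypotheses with the firmest causal footing. It would be judged, if at all, through a test that also requires the marker to track hot flashes. If hypnosis shifts HRV but HRV change is only weakly related to hot flash change, the planned analysis is likely to be null, and a true arm effect could be reported as unsupported. The third mediator, perceived stress, does get an arm model, which suggests an omission rather than a decision.

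A second, smaller matter is precision. If the arm-to-marker path is read off a change score with no baseline covariate, it is estimated less precisely than the same data allow. These two endpoints may also be thin, because the physiologic measures are optional for women with a remote baseline visit (sections 5.1.1 and 5.1.2), and where that applied they are not collected at week 6 (Follow-up Visits).

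**Working it through.** **1. Predictions against planned tests**

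| Marker | Arm difference at week 6 predicted (9.2) | Arm model in 9.7 | Other tests in 9.7 |
|---|---|---|---|
| Perceived stress | H2.2 expects a decrease with hypnosis, at weeks 6 and 12 | Yes, Objective #2 | Indirect effect |
| Cortisol slope | Yes, H2.3 | None | Indirect effect |
| HRV, resting and 24-hour | Yes, H2.4 | None | Indirect effect; baseline HRV as predictor of treatment effect |

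The baseline-HRV test asks who responds to treatment. It does not compare week-6 HRV between arms.

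**2. The plan's own sample size**

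Section 9.3: effect size 0.41, alpha 5%, power 80%, 1:1. A two-sided two-sample t test needs 94.35, rounded up to 95 per arm, or 190; with 18% attrition, 190/(1 − 0.18) = 231.7, or 232. Both figures reproduce and are not in dispute. The 0.41 belongs to the hot flash score. For mediation, section 9.3 asserts adequate power without a calculation.

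**3. Can the indirect-effect test replace the arm test?**

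Simulation: N = 190, 600 runs, percentile bootstrap with 400 draws per run. The marker has unit residual SD and an assumed arm effect of 0.41. The outcome has unit residual SD, a direct arm effect of 0.5, and a marker-to-outcome coefficient b.

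| b | Arm test rejects | Indirect-effect test rejects |
|---|---|---|
| 0 | 80% | 5% |
| 0.1 | 80% | 20% |
| 0.2 | 79% | 58% |
| 0.3 | 80% | 78% |

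The Monte Carlo standard error near 80% is √(0.8 × 0.2/600) = 1.6 percentage points. The arm effect is the same in every row. The indirect-effect result is driven by b, on which the arm component makes no claim.

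**4. Precision of a change score against baseline adjustment**

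With equal variances at baseline and week 6 and correlation ρ, in units of the week-6 variance:

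- change score: 2(1 − ρ)
- week-6 value adjusted for baseline: 1 − ρ² = (1 − ρ)(1 + ρ)
- ratio, adjusted to change: (1 + ρ)/2

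The documents give neither ρ nor an effect size for these markers. Assuming 0.41 SD and 95 per arm (normal approximation):

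| ρ | Variance ratio | Power, change | Power, adjusted | Total N for 80%, change | Total N for 80%, adjusted |
|---|---|---|---|---|---|
| 0.2 | 0.60 | 61% | 82% | 300 | 180 |
| 0.3 | 0.65 | 67% | 84% | 262 | 170 |
| 0.5 | 0.75 | 81% | 90% | 188 | 142 |
| 0.7 | 0.85 | 95% | 98% | 114 | 96 |
| 0.8 | 0.90 | 99.4% | 99.7% | 76 | 68 |

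The unadjusted week-6 value needs 188 at any ρ, so below ρ = 0.5 the change score does worse than not using the baseline at all.

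**5. If fewer women supply samples**

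With an assumed 0.4 SD and ρ = 0.5 (t test), power is 78% on change scores and 89% adjusted at 95 per arm. At an assumed 60 per arm it is 58% and 71%.

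**The case against.** Four counter-arguments have force.

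First, both hypotheses also contain a link with hot flash reduction. If hypnosis shifts HRV and HRV does not track hot flashes, part of H2.4 as written does fail, and the indirect-effect test bears on that part. This stands. A reader might infer that H2.3 and H2.4 are pure arm hypotheses left wholly unexamined; section 9.2 does not support that. What is missing is a test of one component.

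Second, a reader might infer that within-subject change ignores the baseline or biases the comparison. It does neither: it uses the baseline by subtraction and is unbiased under randomisation. The cost is precision and sensitivity to chance imbalance. As the mediator-model covariates are not stated, adjustment is not ruled out either. Nor is the cortisol value necessarily on the original scale, given the conditional log transformation.

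Third, a mediation fit estimates an arm-to-marker path internally. That is true, but the plan commits only to ACME and ADE, so this path is neither a named test nor a promised estimate.

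Fourth, the synopsis treats these mediators as exploratory, and sections 1.2 and 9.2 say they will be explored. This limits the weight of the point. It does not supply the missing comparison, and section 9.6.2 describes both markers among the secondary outcomes.

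**Conclusion.** The point holds for the arm component. H2.3 and H2.4 each predict a week-6 arm difference, section 9.7 specifies no analysis that estimates it, and the indirect-effect test answers a joint question. With an assumed arm effect of 0.41 SD and 190 women, the indirect test rejects between 5% and 78% of the time as b runs from 0 to 0.3, against about 80% for the arm test. Those figures show that the tests address different hypotheses; the gap should not be read as power lost on one hypothesis.

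The precision point is secondary and depends on ρ: material at 0.3 (67% against 84% power), small at 0.7 (95% against 98%). All of this assumes equal variances and values of ρ, effect size and b that the documents do not give.

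A reader might infer that the trial's main conclusion is at risk. It is not: the primary analysis of the hot flash score does not use these markers. The change is worth making because it is cheap and prevents an avoidable misreading of two stated hypotheses.

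**What to change.** Add to Objective #3 in section 9.7:

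- The arm component of H2.3 and H2.4 is estimated from a linear model of the week-6 marker on arm, the baseline value of the same marker, site and participant subgroup (the two randomisation factors), with a 95% confidence interval, reported separately from ACME and ADE.
- The model is applied to cortisol slope and to HRV indices named in advance for the resting and the 24-hour recordings. Section 9.7 lists two indices (SDNN and RMSSD), so the choice has to be written down before data are seen.
- The mediation analysis, and the hot-flash-reduction component of both hypotheses, stay as exploratory analyses, with the mediator-model covariates stated.

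The cost is a few sentences and several regressions on data already being collected. There is a small downside: more exploratory tests. If both indices are used for both recording types and the two supine recordings are combined, there are 1 + 2 × 2 = 5 contrasts. Were they independent and all null, the chance of at least one result below 5% would be 1 − 0.95⁵ = 23%. They should therefore be labelled exploratory, or one HRV index chosen per recording type, which leaves three. The text should be fixed before database lock, when the statistician and PIs are unblinded (section 6.2.3, Blinding).

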1.2 Secondary Objectives

Secondary objectives are to evaluate the efficacy of the self-administered hypnosis compared to self-administered sham white noise hypnosis for hot flash activity interference, sleep disturbance, anxiety and perception of benefit; with the expectation that there will be significant improvements among participants in the self-administered hypnosis group when compared with the self-administered sham white noise hypnosis group at 6 weeks. Further, we will evaluate the effects of self-administered hypnosis compared to the self-administered sham white noise hypnosis control at 12 weeks, for all secondary outcomes except perception of benefit.

Hypothesis 2.1

Compared to self-administered sham white noise hypnosis control, the self-administered hypnosis intervention will result in significant improvements in hot flash activity interference, sleep disturbance, and anxiety at 6 and 12 weeks, and perception of benefit at 6 weeks.

Additionally, mediators (perceived stress, cortisol, and heart rate variability (HRV) and moderators (hypnotizability and practice adherence) of hot flash reduction will be explored to address the following hypotheses:

Hypothesis 2.2

A decrease in perceived stress will be indicated in the self-administered hypnosis group due to the intervention, which will correspond and contribute to further decrease of the hot flash score at 6 and 12 weeks.

Hypothesis 2.3

Diurnal salivary cortisol will demonstrate better circadian rhythms (steeper slopes) in those with larger hot flash reductions and in the self-administered hypnosis group compared to participants in the self-administered sham white noise hypnosis at 6 weeks.

Hypothesis 2.4

Self-administration of hypnosis and greater hot flash reductions will result in higher resting and 24-hour parasympathetic activity, reflected as higher HRV at 6 weeks.

Hypothesis 2.5

Higher hypnotizability scores and better adherence rates will be associated with greater reductions in hot flash scores in the self-administered hypnosis group.

Hypothesis 2.6

Self-administered hypnosis will significantly decrease vasomotor symptoms (hot flash score of

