The ambulatory device will be returned to the investigators in a pre-posted mailer immediately following each HRV data collection (i.e., baseline and week 6 endpoint). Data will be downloaded as soon as it is received in the lab, for optimal resolution and to protect privacy. The device will then be cleared of data and available for the next use, which should ensure that study recruitment is not delayed due to a shortage of Polar V800 devices.

Heart rate variability monitoring is explained in the baseline visit. During the COVID-19 restrictions, this interaction will occur by telephone or video conference. If the participant is unable to demonstrate understanding of the collection process, we will not collect heart rate variability on that participant in the study. Additionally, if there is any interruption to mail service, this portion of the study will be paused during COVID-19 restrictions.

Perceived Stress Scale (PSS)

The PSS contains 10 items that measure the degree to which situations in one's life are appraised as stressful. [94] The scale provides the degree to which individuals find their lives to be unpredictable, uncontrollable, and overloaded, as well as measures the current levels of experienced stress. [95] Items are scored on a scale from 0-4 with higher scores reflecting more perceived stress. This measure has been shown to be valid and internally consistent, with an alpha of .83. [94] This will be completed at baseline, 6, and 12 weeks.

[name] Hypnotizability Scale (EHS)

The EHS is a 12-item, research assistant-administered, scale for rating hypnotizability in the general population. Each item is rated pass\fail, with higher scores indicative of greater hypnotizability.

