6.2.3 Follow-up Visits

Week 1-6: Eligible participants will be randomly allocated to either a self-administered hypnosis group or a self-administered sham white noise hypnosis control group. Both groups will meet with a study research assistant two times (at baseline and at randomization/education visit) in person (or by telephone or video conference during COVID-19 restrictions) and further contact will be by phone through week 6 of the intervention period.

The interventions will be delivered through pre-recorded digital audio files, flash drives or CD's. For participants who prefer a flash drive or CDs, those will be provided. Additionally, if a participant prefers to use CDs, but does not have a CD player, one will be provided. Prepared self-management booklets will also be provided to each participant.

Participants in the self-administered hypnosis group and the self-administered sham white noise hypnosis group will use the self-management materials (booklets and audio recordings) for six weeks. A second kit to collect saliva and a Polar V800 HRV monitor will be mailed to participants during week five to be used for Week 6 data collection. At the end of Week 6, they will collect two days of saliva samples. HRV data will also be collected during the two days of saliva collection (as done during the baseline week) and both will be returned immediately following collection via a pre-posted mailer. However, if this collection was optional or unable to be completed due to COVID-19 restrictions, saliva samples and HRV data will not be collected at this time. At the end of Week 6, participants will return the completed hot-flash daily diaries, the self-hypnosis practice log, the questionnaire booklet with outcome measures of daily activity interference, quality of life, sleep disturbance, anxiety and stress in the provided pre-posted mailer. Due to COVID-19 restrictions, participants will also have the option of returning materials electronically (e.g., through DocuSign).

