9.7 Data Analyses

In general, we will conduct an intent-to-treat (ITT) analysis in which all participants randomized to a treatment condition will be analyzed as such regardless of noncompliance, withdrawal, etc. A common strategy for ITT analysis when participants withdraw from a study is to carry the last observation forward. Given the likely underestimation of the variability due to that approach, we will employ multiple imputation to address missing data. We will also analyze the data based on completers and for those who have primary endpoint data at 6 weeks. We will explore the differences in the outcomes; and also explore which characteristics are present in those who do and do not have primary endpoint data. (See section 9.6, missing data).

Objective #1

The primary outcome will be change in hot flash scores over time during the treatment weeks (Weeks 1-6) compared to baseline between groups. Seven hot flash scores will be used (i.e., baseline score + weekly score for weeks 1 through 6) for each group. Hot flash scores will be used as the dependent variable in a longitudinal regression model that accounts for both group assignment as well as changes across the seven measurement points. The effective number of observations for this model is 1,624 observations (232 participants × 7 hot flash scores = 1,624). A second model will be constructed to include the week 12 (follow-up) data, which is an 8th observation for each participant to evaluate treatment sustainability as a secondary outcome. The effective number of observations for the model is 1,856 observations (232 participants × 8 hot flash scores = 1,856). The effect of the hypnosis intervention will be determined in these models by the difference between the changes hot flash scores (i.e., slopes) between the hypnosis and control groups. Important potential confounder variables (e.g., race/ethnicity, education, etc.) can easily be included in these models to account for their effects. The model described above is shown algebraically below.

```
Level 1 Model:
Y_{ti} = \pi_{0i} + \pi_{1i} a_{ti} + e_{ti}
Y_{ti} = Hot flash score at time t for participant i
\pi_{0i} = Intercept (average) hot flash score at baseline
\pi_{1i} = Amount of change in hot flash score associated with time t
a_{ti} = Value of time t
e_{ti} = Random error in hot flash score at time t for participant i [e_{ti} \sim N(0, \sigma^2)]
Level 2 Model:
\pi_{0i} = \beta_{00} + \beta_{01} X_1 + r_{0i}

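### At week 6 the mediators are measured with or after the outcome they should explain, so the planned mediated share cannot be told apart from reverse causation or a shared cause

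*Combined protocol and SAP*

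**What the plan says.** Section 9.7 sets the direction of the mechanistic aim, with the hot flash outcome at the end of the path: "The focus of Aim #3 is to determine the extent to which cortisol levels, HRV, and perceived stress mediate the relationship between group assignment". The mediators are change scores: "Within-subject change in HRV, cortisol slopes and perceived stress scores will be tested as mediators". The estimand is causal and applies to primary and secondary outcomes alike: "Average causal mediation effects (ACME) and average direct effects (ADE) will be calculated to compare the mediated and un-mediated portion".

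Timing comes from several places:

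- Cortisol (Section 6.2.3, Follow-up Visits): "At the end of Week 6, they will collect two days of saliva samples". Section 10.1 confirms that physiologic measures are taken at baseline and week 6 only.
- HRV (Section 9.7): "These measures cover both short and longer term recordings and will be collected at baseline and the end of the intervention, week 6".
- Perceived stress (Section 6.2.2.2): "This will be completed at baseline, 6, and 12 weeks".
- Primary outcome (Section 9.7): "The primary outcome will be change in hot flash scores over time during the treatment weeks (Weeks 1-6) compared to baseline between groups".

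On direction, Hypothesis 2.4 (Sections 1.2 and 9.2) says: "Self-administration of hypnosis and greater hot flash reductions will result in higher resting and 24-hour parasympathetic activity".

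**The concern.** A mediation claim needs the mediator to change before the outcome does. Here the only post-randomisation HRV and cortisol values come when the six weekly diary scores are complete or nearly so. The week-6 stress scale sits in the same booklet as the week-6 secondary outcomes. If fewer hot flashes lead to calmer days and higher HRV, or if a third factor improves both, the product of the two regression paths is non-zero although nothing is mediated.

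The plan's own hypotheses show that this is not far-fetched: Hypothesis 2.4 asserts the reverse path. Yet Objective #3 names no lag, outcome week, identifying assumption or sensitivity analysis. It justifies the bootstrap by power and freedom from normality, neither of which bears on direction. Randomisation protects the arm-to-mediator comparison but not the mediator-to-outcome one. The trial could report a percentage of benefit explained by autonomic or stress change that its data cannot establish.

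**Working it through.** **1. Order of measurement**

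| Variable | After randomisation | Relative to weeks 1-6 diary |
|---|---|---|
| Cortisol slope | end of week 6 | with or after |
| HRV | end of week 6 | with or after |
| Perceived stress | weeks 6 and 12 | first value with or after |
| Week-6 questionnaires | week 6 | same booklet as stress |
| Week-12 diary | week 12 | later than the week-6 mediators |

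**2. Direction**

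- Section 3 (conceptual framework) and Section 9.7: arm → autonomic or stress change → hot flashes.
- Hypothesis 2.2: stress contributes to the fall in hot flash score (same direction).
- Hypothesis 2.3: cortisol slopes go with hot flash reduction and with arm (association only).
- Hypothesis 2.4: arm and hot flash reduction → HRV (reverse direction).

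**3. The plan's own figures.** Section 9.3 gives no mediation calculation; it only says the sample size should suffice. With d = 0.41, two-sided 5%, the exact t calculation gives 95 per arm, total 190, power 0.803. Then 190/(1 − 0.18) = 231.7, hence 232. Both figures reproduce. The section's simulated means and SDs give a strictly standardised difference of 5.8/√(9.8² + 9.9²) = 0.42, close to the stated 0.41. On the ordinary SD scale 0.41 becomes 0.41 × √2 = 0.58. I use 0.41 and 0.58 as the range of arm effects.

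**4. Apparent share with no mediation at all.** Let Y be hot flash reduction and X the arm, with Y = dX + e and Var(e) = 1. Let the mediator change be caused only by Y: M = rY + √(1 − r²)·u. Here r is the within-arm correlation and is **my assumption**.

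- Arm on mediator: a = rd.
- Mediator on outcome given arm: b = Cov(M,Y|X)/Var(M|X) = r/(r² + 1 − r²) = r.
- ACME = ab = r²d; total effect = d; apparent share = r².

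So r = 0.3, 0.4, 0.5 gives 9%, 16%, 25%, although the true share is 0.

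**5. How often it would be significant.** With 95 per arm, SE(a) = √(2/95) = 0.145. The b path is nearly always significant: at r = 0.3, z = 0.3/√(0.91/187) = 4.3. The a path therefore governs.

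| d | r | a = rd | z = a/0.145 | P(significant) |
|---|---|---|---|---|
| 0.41 | 0.3 | 0.123 | 0.85 | 13% |
| 0.41 | 0.5 | 0.205 | 1.41 | 29% |
| 0.58 | 0.3 | 0.174 | 1.20 | 22% |
| 0.58 | 0.5 | 0.290 | 2.00 | 52% |

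Simulations of the same model, with N = 190 and interval estimates of the ACME, gave roughly 14% to 54% over this range.

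**6. Why the data cannot decide.** A partial-mediation model with a = rd, b = r and direct effect d(1 − r²) implies exactly the same covariances among arm, mediator and outcome as the pure reverse model in step 4. More resampling does not separate them.

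**7. Moving the outcome to week 12 with adjustment for the week-6 score.** Under pure reverse causation this model gives almost no false positives (0% to 1% of simulated trials). Now suppose mediation is real but acts during weeks 1 to 6: M → week-6 score → week-12 score. Given the week-6 score, M says nothing more about week 12, so b = 0 and the ACME is 0 again. With 30% to 50% of the week-6 effect truly mediated and an assumed carry-over of 0.8, the adjusted model was significant in about 0.3% to 2.5% of simulated trials, against 66% to 98% for the week-6 analysis. Other assumed settings gave about 3% to 5% against 97% to 98%. Its silence is not evidence against mediation.

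**The case against.** The strongest reply has four parts.

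- **Exploratory status.** The synopsis labels the mediator analyses exploratory and the primary test does not depend on them. This stands and limits the severity. It does not dispose of the point: mechanism is one of three stated purposes in Section 2.2, and Section 9.7 plans a null-hypothesis test and a causal share.
- **Only one hypothesis is out of line.** This also stands. A reader might infer that Hypothesis 2.3 reverses the direction too. It does not: its wording is associational, and Hypothesis 2.2 runs in the mediation direction.
- **Not every outcome precedes the mediators.** Correct. Section 9.7 covers secondary outcomes, and the week-12 hot flash score follows the week-6 mediators. But Objective #3 does not tie the mediation model to week 12, and an unadjusted week-12 model inherits the problem. In simulation (arm effect 0.41 SD, carry-over 0.8) it was falsely significant in about 7% of trials at r = 0.3 and 34% at r = 0.5.
- **The sizes rest on an assumed correlation.** True. At r = 0.2 the apparent share is only 4% and significance about 8%, close to nominal. The figures illustrate; they do not predict.

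A reader might also infer that the week-12 model adjusted for week 6 should replace the planned analysis. Step 7 shows why not: it conditions on a treatment-affected variable and answers a different question.

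**Conclusion.** The concern holds for the week-6 outcomes. The planned ACME and mediated share cannot be distinguished from reverse causation or a shared cause, and the plan contains no safeguard. With no true mediation, an assumed within-arm correlation of 0.3 to 0.5, 190 women and an arm effect of 0.41 to 0.58 SD, about 9% to 25% would appear mediated, significantly so in roughly 14% to 54% of trials. The share depends only on the assumed correlation; the significance rates also depend on arm effect and sample size.

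The documents do not support the stronger reading that mediation is absent or disproved. A week-6 value may reflect a shift that began earlier. The design simply cannot show which came first. The point should be addressed before analysis, but it does not touch the efficacy conclusion.

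**What to change.** In Section 9.7, Objective #3:

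1. Name the outcome week, and report the week-6 mediator-outcome relation and any mediated share as an exploratory association, not a causal proportion.
2. Accompany any ACME with a sensitivity analysis for mediator-outcome confounding, giving the residual correlation at which the ACME reaches zero. In the illustration above that would be r itself, 0.3 to 0.5.
3. Report the reverse-direction model (arm → hot flash change → mediator) alongside. It will not settle direction, but it shows whether the evidence is symmetric.
4. Reconcile Hypothesis 2.4 (Sections 1.2 and 9.2) with Section 3 and Section 9.7 so that one direction is hypothesised.
5. If wanted, add a week-12 model adjusted for the week-6 score, labelled as supplementary and as addressing additional effect after week 6 only.

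Cost: wording and a little more analysis, with no new data. The price is a weaker mechanistic claim.
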